3.5.2 Restrictions

3.5.2.1 Asthma medication restrictions

(a) Asthma medication restrictions on the days of scheduled spirometry visit

Pre- and/or post-dose spirometry assessments will be performed at the study center at scheduled visits (see [Table 1](#) and [Table 2](#)): restrictions to patient's background

asthma medication are required prior to the spirometry as described below (also see Section 5.1.2):

Treatment Visits 1–14 (Visits 1-27 for adolescents):

Twice daily ICS and LABA therapies should be withheld for 12- 24 hours; once daily therapies containing ICS, LABA, or LAMA therapies should be withheld for ≥ 24 hours before scheduled center visit spirometry as this will affect the pre-BD FEV₁ value; they may be taken subsequently, at the center. For the same reason patients should not use their rescue SABA medication (albuterol/salbutamol/levalbuterol) within 6 hours of a scheduled center visit spirometry. This restriction is particularly critical for efficacy measures taken during the treatment period.

If the patient has taken their usual ICS-LABA asthma controller medication on the morning of the scheduled spirometry visit, the Investigator/authorized delegate should remind the patient of the importance of withholding their usual morning asthma medication, and reschedule the visit for another day within the allowed window.

If the patient has taken rescue SABA within 6 hours of the planned center visit spirometry they should ideally

- 1) remain at the center until such time that the 6 hour withholding time has been reached if it does not exceed the 1.5 hour spirometry window or
- 2) return on another day, within the visit window.

(b) Asthma medication restrictions on unscheduled visits

Asthma medication restrictions on unscheduled visits may not be feasible and may be applied at the discretion of the Investigator. Timing of recent controller and rescue SABA use relative to the unscheduled spirometry should be noted in the record.

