5. STUDY ASSESSMENTS AND PROCEDURES

5.1 Efficacy assessments

5.1.1 Assessment of asthma exacerbations

Although this is a safety study, asthma exacerbations will be assessed to characterize the exacerbation rate with longer maintenance treatment. In this study, an asthma exacerbation is defined as a worsening of asthma which requires use of systemic corticosteroids for at least 3 days, and/or an in-patient hospitalization, and/or emergency department or urgent care visit.

An asthma exacerbation that occurs ≤ 7 days following the last dose of systemic steroids (oral, IM, IV), prescribed for a prior exacerbation, will be counted as the same exacerbation event.

The patient may remain in the study after an exacerbation and continue to receive IP if the Investigator judges that it is medically appropriate for the patient to do so.

Study center evaluations for asthma worsening may occur as an unscheduled visit or as part of an ordinary center visit if the worsening happens to be coincident with a scheduled visit window. A copy of the medical record should be obtained for exacerbations evaluated and treated at non-study centers (eg, by the primary care HCP or at an emergency department/hospital) and details entered into the exacerbation eCRF in a timely fashion. Changes in concomitant medication due to exacerbation must be recorded in the appropriate module of the eCRF.

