5.1.2 Spirometry

General requirements

Lung function (FEV₁ and FVC) at the study center will be measured by spirometry using the site's own equipment. Spirometry will be performed by the Investigator or authorized delegate according to American Thoracic Society/European Respiratory Society (ATS/ERS) guidelines. (Miller et al 2005).

The Investigator is responsible for assuring that the spirometer used at the site meets ATS/ERS recommendations and that the study center personnel performing the testing are properly trained and certified. In order to minimize variability, the same spirometer should be used for all assessments of spirometry on patients in this study, wherever possible. If there is any need to change the device, AstraZeneca should be notified. Calibration of spirometers must be performed in accordance with the instructions of the manufacturer and should be performed every time a study subject visits the study center. All calibration reports must be signed, dated and filed in the Investigator Study File (ISF).

Important! Patients should withhold their usual ICS and long-acting bronchodilator containing medications on the morning of the Visit 1 FEV₁ measurement and post-bronchodilator testing. Twice daily ICS and long-acting bronchodilator therapies should be withheld for 12- 24 hours; once daily therapies containing ICS, LABA, or LAMA therapies should be withheld for ≥ 24 hours before scheduled center visit spirometry as this will affect the pre-BD FEV₁ value; they may be taken subsequently, at the center. For the same reason patients should not use their rescue SABA medication (albuterol/salbutamol/levalbuterol) within 6 hours of a scheduled center visit spirometry. This restriction is particularly critical for efficacy measures taken during the treatment period.

Options for handling patients who have inadvertently taken their asthma medication within the restricted window are described in Section 3.5.2.

All patients transitioning from the OCS-sparing study (ZONDA) into this study are exempt from performing the post-BD assessments. The pre-BD measurement from EOT for ZONDA patients will serve as the first pre-BD measurement for these patients in BORA.

Time of day for scheduled center visit spirometry

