2.3 Adjusted visit window definitions

For the exacerbation-related analyses, no windows will be applied. For local electrocardiogram (ECG), vital signs, Work Productivity and Activity Impairment Questionnaire plus Classroom Impairment Questions (WPAI+CIQ), and post-bronchodilator spirometry, the visit recorded in web-based data capture (WBDC) will be used. For other visit-based data the variables will be summarised based on the collection study days with adjusted visit windows.

The adjusted analysis-defined windows will be based on the collection schedule listed in the protocol, and collected assessments will be windowed to the closest scheduled visit for the variable of interest. Visit windows have been constructed so that every observation collected can be allocated to a particular visit. The adjusted windows are summarised in [Table 2 – Table 8 in Appendix A](#) [Analysis visit windows](#)

For assignment of data to adjusted analysis-defined visit windows, study day is defined as follows:

$$(Date\ of\ assessment - date\ of\ first\ dose) + 1$$

By this definition, the day of first dose will be Study Day 1 and the planned date of Visit 2 (Week 4) will be Study Day 29 (=28+1), for example.

If multiple readings are recorded within a single adjusted visit window, in general, the following rules will be applied:

- If there are 2 or more observations within the same adjusted visit window, then the non-missing one closest to the scheduled study day will be used in the analysis.
- If 2 or more observations are equidistant from the scheduled study day, then the non-missing observation with the earlier collection date will be used in the analysis.
- If 2 or more observations are collected on the same day, then the non-missing one with the earlier collection time will be included in the analysis.

If an adjusted visit window does not contain any observations, then the data will remain missing.

For the overall analyses that are not based on any particular study visit, all data will be listed and/or analysed, including any repeat or unscheduled visits, unless otherwise specified. For example, for safety summaries, all post-baseline results will be included in the overall analysis up to and including the FU visit.

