| Week 0 | 1 | Study Day \leq 1 |
| Week 12 | 85 | 2 \leq Study Days \leq 238 |
| Week 56 (EOT for adults) | 393 | 239 \leq Study Days \leq 574 |
| Week 108* (EOT for adolescents) | 757 | 575 \leq Study Days |

For chemistry labs: Calcium, Chloride, CO₂, Glucose, Phosphorus, Potassium, Sodium, Total cholesterol and Uric acid.

* Visits for adolescents only.

Table 7 Adjusted visit windows for PK (unscheduled samples only) and ADA (including nAb)

| Analysis Visit | Scheduled study day | Adjusted visit window |
|---------------------------------|----------------------------|----------------------------------|
| Week 0 | 1 | Study Day \leq 1 |
| Week 8 | 57 | 2 \leq Study Days \leq 84 |
| Week 16 | 113 | 85 \leq Study Days \leq 154 |
| Week 28 | 197 | 155 \leq Study Days \leq 252 |
| Week 44 | 309 | 253 \leq Study Days \leq 336 |
| Week 52 | 365 | 337 \leq Study Days \leq 385 |
| Week 56# (EOT for adults) | 393 | 386 \leq Study Days \leq 434 |
| Week 68# (FU for adults) | 477 | 435 \leq Study Days |
| Week 60* | 421 | 386 \leq Study Days \leq 476 |
| Week 76* | 533 | 477 \leq Study Days \leq 588 |
| Week 92* | 645 | 589 \leq Study Days \leq 700 |
| Week 108* (EOT for adolescents) | 757 | 701 \leq Study Days \leq 798 |
| Week 120* (FU for adolescents) | 841 | 799 \leq Study Days |

Visit for adult only.

* Visits for adolescents only.

Note that the Week 52 window has a shorter window range (3 weeks) post scheduled study day due to adjustment for adult group having a scheduled EOT visit 4 weeks later.

Table 8 Adjusted visit windows for Pre-BD spirometry

| Analysis Visit | Scheduled study day | Adjusted visit window |
|---------------------------------|---------------------|----------------------------------|
| Week 0 | 1 | Study Day \leq 1 |
| Week 16 | 113 | 2 \leq Study Days \leq 168 |
| Week 32 | 225 | 169 \leq Study Days \leq 280 |
| Week 48 | 337 | 281 \leq Study Days \leq 385 |
| Week 56# (EOT for adults) | 393 | 386 \leq Study Days |
| Week 64* | 449 | 386 \leq Study Days \leq 504 |
| Week 80* | 561 | 505 \leq Study Days \leq 616 |
| Week 96* | 673 | 617 \leq Study Days \leq 728 |
| Week 108* (EOT for adolescents) | 757 | 729 \leq Study Days |

Visit for adult only.

* Visits for adolescents only.

Note that Week 48 window has shorter window range (7 weeks) post scheduled study day due to adjustment for adult group having a scheduled EOT visit 8 weeks later.

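### SAP 2.3 and Table 8 let an unscheduled pre-bronchodilator FEV1 reading stand as a Week 16–56 value, and leave the adult end-of-treatment window open

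*SAP*

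**What the plan says.** SAP 2.3 keeps the visit recorded in the data capture system for ECG, vital signs, WPAI+CIQ and post-bronchodilator spirometry. Pre-BD spirometry is not on that list, so it falls under the next rule: "For other visit-based data the variables will be summarised based on the collection study days with adjusted visit windows". The section adds: "Visit windows have been constructed so that every observation collected can be allocated to a particular visit". When a window holds two or more readings, "then the non-missing one closest to the scheduled study day will be used in the analysis"; if two are equally distant, "then the non-missing observation with the earlier collection date will be used in the analysis".

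The table in SAP Appendix A titled "Adjusted visit windows for Pre-BD spirometry" (Table 8) sets Week 16 at Days 2–168, Week 32 at Days 169–280, Week 48 at Days 281–385, and adult Week 56 at Day 386 onward. The adolescent Week 108 window is likewise open, from Day 729.

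On how readings are taken, Protocol 5.1.2 bars rescue SABA "within 6 hours of a scheduled center visit spirometry. This restriction is particularly critical for efficacy measures taken during the treatment period". For other visits, Protocol 3.5.2.1(b) says: "Asthma medication restrictions on unscheduled visits may not be feasible and may be applied at the discretion of the Investigator". Protocol 5.1.1 adds: "Study center evaluations for asthma worsening may occur as an unscheduled visit".

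**The concern.** A by-visit pre-BD FEV1 table is meant to show lung function at a set time, measured with controllers and rescue medication withheld. The SAP selects on study day alone. It uses neither visit type nor the medication timing that Protocol 3.5.2.1(b) asks sites to note at unscheduled spirometry. Its quality-grade filter (SAP 2.4) is stated for baseline only. A reading obtained under different conditions, weeks from the nominal visit, can therefore be summarised as that visit's value.

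At the end of treatment the label itself can be wrong: with no upper limit on adult Week 56, a reading after treatment has stopped can appear as EOT.

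The endpoint is secondary and is also displayed by ADA status (SAP 4.2.10). If substitutes are more common in patients who worsen, part of the FEV1 summary would reflect exacerbations.

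**Working it through.** The plan gives no figure for this, so the check applies its rules to cases and then sizes the effect under stated assumptions.

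**Window widths (Table 8; target Days 113, 225, 337).** The last column assumes a ±3-day visit window, that is, 7 days.

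| Visit | Window | Days | Furthest reading from target | Days outside ±3 |
|---|---|---|---|---|
| Week 16 | 2–168 | 167 | 113 − 2 = 111 | 160/167 = 96% |
| Week 32 | 169–280 | 112 | 225 − 169 = 56 | 105/112 = 94% |
| Week 48 | 281–385 | 105 | 337 − 281 = 56 | 98/105 = 93% |

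The windows are contiguous, so no post-baseline reading falls outside them.

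**Route 1: scheduled spirometry missing.** An unscheduled reading on Day 20 is the only one in Days 2–168, so it becomes Week 16.

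**Route 2: scheduled spirometry present but off target.** With the scheduled reading on Day 116 (distance 3), an unscheduled reading on Days 111–115 is nearer, and one on Day 110 wins the tie as the earlier date: 6 days in all. For scheduled readings 3, 2 or 1 days early, the displacing days number 5, 3 and 1; for 1, 2 or 3 days late, they number 2, 4 and 6. With the scheduled reading exactly on Day 113 there are none.

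**Route 3: after EOT.** If EOT spirometry is missing, any later reading qualifies as adult Week 56. An adult last dosed on Day 365 (Week 52) leaves the on-treatment period of SAP 3.1.1 by Day 365 + 28 + 7 = 400 at the latest, yet Table 8 accepts Day 401 and beyond. SAP Table 3 closes adult Week 56 at Day 434 for ACQ-6 and AQLQ(S)+12.

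**How often, Week 16, route 1.** Assumptions, none from the documents:
- 0.4 to 1.0 exacerbations per patient-year, as a Poisson process
- every exacerbation measured at an unscheduled visit
- 5% to 15% of Week 16 spirometry missing, independently of worsening

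P(at least one event in 167 days) = 1 − exp(−r × 167/365.25):
- r = 0.4: 16.7%; × 5% = 0.8% of patients
- r = 1.0: 36.7%; × 15% = 5.5% of patients

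As a share of values analysed, these become 0.0084/(0.95 + 0.0084) = 0.9% and 0.055/(0.85 + 0.055) = 6.1%.

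The upper rate is probably too high. The SAP Amendment History drops the Kaplan–Meier median for former placebo patients because exacerbations are expected to be too few to estimate it. At r = 1.0, 1 − exp(−392/365.25) = 66% would have an event by Week 56, so the median would be estimable. A median beyond 392 days implies r below ln 2 × 365.25/392 = 0.65. At that rate, 25.6% × 15% = 3.8%.

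**Size in mL.** Shift in the visit mean = share of substitutes × difference per reading. Assuming shares of 1% to 10% and differences of −0.5 to +0.3 L, the shift ranges from 0.10 × (−0.5 L) = −50 mL to 0.10 × 0.3 L = +30 mL. At 3% and −0.3 L it is −9 mL. A 10% share is one value in a cell of ten.

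**The case against.** The case against has four parts.

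- **Scheduled readings may be intended.** SAP 3.2.2 ties the FEV1 variable to visits as scheduled in the protocol tables, and SAP 2.3 names unscheduled visits only for analyses not tied to a visit. This supports an intention but states no exclusion, and the allocation sentence points the other way. Table 7 windows unscheduled PK samples, so windowing in this SAP does not imply scheduled data only. Two programmers could reasonably differ.
- **An on-time scheduled reading nearly always wins.** This stands. A reader might infer that scheduled values are routinely replaced, but every displacing day in route 2 lies within Days 110–116. Protocol 4.2.3.4 and 5.1.1 allow worsening in that window to be handled at the ordinary visit. The main route is missed spirometry.
- **The readings need not be contaminated.** This also stands. A reader might infer that substitutes are bronchodilated exacerbation values arising only in patients who worsen. The protocol makes withholding discretionary, not absent, and the schedule-table footnotes allow unscheduled visits as needed, for any reason.
- **Dropping readings has its own bias.** SAP 4.1 includes all captured data irrespective of protocol adherence, and the SAP Amendment History says that windows follow the rules of the pivotal studies. Leaving a window empty may remove values mainly from patients who worsened, which could flatter mean FEV1. This is a fair cost and belongs in the remedy. A visit-type filter would also keep exacerbation readings taken at scheduled visits, although withholding applies there.

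On the open window, Protocol Section 2 words the lung-function objective as running through follow-up, unlike 8.4.1 and 8.4.1.3. Even on that wording, a follow-up reading should not carry the EOT label.

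**Conclusion.** The gap is real on the written rules, and minor. Pre-BD FEV1 is windowed by study day with no exclusion of unscheduled visits, so a reading that may lack withholding can be analysed as a Week 16–56 value, chiefly when scheduled spirometry is missing. The open adult Week 56 window conflicts with Protocol 8.4.1 and 8.4.1.3.

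The 0.8% to 5.5% is an assumption-driven range, not an estimate. Measuring every worsening at the site pushes it up, because Protocol 5.1.1 expects some to be treated elsewhere. Treating missed spirometry as unrelated to worsening may push it down; by this route the share of patients cannot exceed the fraction with missing scheduled spirometry. The direction is mixed, since worsening lowers FEV1 and bronchodilator raises it.

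The study tests no powered hypothesis, and FEV1 is summarised descriptively. A reader might infer that the overall FEV1 conclusions are unsafe; the documents do not support that. The practical exposure is in small cells, such as adolescents and ADA subgroups, where one or two values can move a mean.

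**What to change.** In SAP 2.3 and Table 8:

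- State that by-visit pre-BD FEV1 uses only spirometry from scheduled, EOT and IPD visits. If a window holds none, leave it missing.
- List unscheduled spirometry separately.
- Close the adult Week 56 window at EOT or the end of the on-treatment period defined in SAP 3.1.1, and treat the adolescent Week 108 window in the same way.
- Add one sensitivity summary of by-visit pre-BD FEV1 that includes the unscheduled readings.

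The cost is a few lines of SAP text, one filter on visit type, one window limit and one extra table, with no new data. Slightly more values will be missing, possibly concentrated in patients who worsened; the sensitivity summary shows whether that matters.

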2.4 Baseline and change from baseline

In general, the last non-missing value on or prior to the first dose of IP in BORA will be used as the baseline. The last evaluable post-dose record from the predecessor studies will also be

considered in the selection of baseline value for BORA study. If there is no assessment present, then the baseline value will not be imputed and will be set as missing. Exceptions for both pre-bronchodilator (pre-BD) and post-bronchodilator (post-BD) FEV₁ as specified below.

For pre-BD FEV₁, the following hierarchy rules will be applied to derive baseline:

- Step 1: Select values with acceptable quality (acceptable or borderline quality grade) on the same date closest to the first IP dose in BORA. If the assessments are on the same day of the first IP dose, only the assessments on or prior to the IP dose are used.
- Step 2: If there are central and local spirometry assessments on the same day, central spirometry assessments will be used.
- Step 3: If there are multiple assessments with different times, the earliest assessment will be used.
- Step 4: If there are multiple assessments with the same date and time, the value recorded in the BORA study database will be used.

For post-BD FEV₁, the baseline will be derived independently from pre-BD FEV₁ assessments. With exception from Step 2 to select the highest value within central or local spirometry, the same hierarchy rules as explained above will be applied.

Change from baseline will be calculated as the post-baseline assessment value minus the baseline assessment value. If either value is missing, then the change from baseline value will be missing.

2.5 Prior/Concomitant medications

Medication will be classified as a maintenance asthma medication at baseline if it started prior to or on the date of first dose of IP in BORA and was ongoing after the first dose of IP. Inhaled corticosteroid (ICS) doses will be converted to their Fluticasone Propionate dry powder equivalent in micrograms. Oral corticosteroid (OCS) doses will be converted to their Prednisolone equivalent in milligrams.

An asthma medication will be regarded as prior if it was stopped on or before the date of first dose for the study (medication stop date \leq date of the first dose).

Medication will be regarded as concomitant if the start date is after the date of first dose in BORA, or if it started prior to the date of first dose and was ongoing after the date of first dose. Medications with start date after the on-treatment period (as is defined for adverse events in Section 3.1.1) will not be considered as a concomitant.

Medications recorded in the predecessor studies that were ongoing or stopped after the first dose of BORA are integrated with BORA data for summaries.

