4.1 Enrolment period

4.1.1 Randomization (Visit 1)

Each potential patient or parent/legal guardian (as applicable) will provide written informed consent prior to any study specific procedures and undergo assessments applicable for the visit (see [Table 1](#) or [Table 2](#)).

In order to provide sufficient time for patients to consider participation in this study, and to ensure an uninterrupted dosing regimen as patients transition between the predecessor study and this study, patients will be provided with the ICF at/after the visit at which they receive their last dose of IP in the predecessor study and will be asked to sign the ICF at Visit 1 of this study, prior to any study-specific procedures being performed.

Visit 1 of this study will be scheduled to ensure an uninterrupted dosing regimen as patients transition between the predecessor study and this safety extension study. Therefore, if the actual EOT visit in the predecessor study occurs more than 7 days from the scheduled EOT visit, the patient will not be eligible to enrol in this study. The End-of-Treatment (EOT) visit for the predecessor study and Visit 1 for this study will occur on the same day and will include the first dose of IP for this study. If IP cannot be administered at this visit, the patient will not be eligible for enrolment in this study.

As Visit 1 coincides with the EOT visit of the predecessor study, repeated assessments (see [Table 1](#) and [Table 2](#)) are not required, as data will be duplicated programmatically between the 2 study databases, as applicable. As electronic patient-reported outcome (PRO) devices were used to capture ACQ6, AQLQ(S)+12, WPAI+CIQ, EQ-5D-5L in the predecessor studies, the patient does not need to complete the paper versions of these at Visit 1 of this safety extension study.

Registration of patient's enrolment via IWRS/IVRS should occur on day when other Visit 1 procedures are done.

Visit 1 assessments are primarily concerned with confirmation of the patient eligibility for the extension study

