4.2.3 Concomitant medication

The number and percentage of patients who take concomitant medications, and those who take disallowed concomitant medications during the study, will be presented by treatment group. Concomitant medications will be classified according to the AstraZeneca Drug Dictionary (AZDRUG). The summary tables will present data by generic term within ATC code.

The number and percentage of patients taking maintenance asthma medications, including ICS/LABA fixed dose combinations, at baseline will be summarised and for those patients taking ICS and OCS at the study baseline, the converted dose will be summarised. The number of patients treated with ICS and OCS at baseline will be summarised separately by ATC code and preferred term, with total daily dose (non-converted) at baseline summarised for each preferred term. A similar summary will be prepared to summarise total daily dose of OCS at baseline. For patients from ZONDA, all OCS taken at baseline regardless of reason for therapy will be included to be consistent with the way the data was reported and analysed in ZONDA.

All above summaries also will be summarised for the patients who rolled over to MELTEMI study.

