8.2 Appendix B Partial and missing date imputation

Dates missing the day or both the day and month of the year will adhere to the following conventions in order to classify on-treatment AEs and to classify prior/concomitant medications.

For AE start date or medication start date:

Partial missing start date:

- Missing day of the month: 1st day of the month
- Missing day and month: Jan. 1st of the year

Completely missing start date:

- If AE end date or medication end date is missing, then impute the start date as the first visit date (Visit 1)
- If AE end date or medication end date is before the first visit date (Visit 1), then impute the start date as the end date
- If AE end date or medication end date is after the first visit date (Visit 1), then impute the start date as the first visit date (Visit 1)
- Otherwise, impute the start date as the first visit date (Visit 1)

For AE end date or medication end date:

Partial missing end date:

- Missing day of the month: Last day of the month
- Missing day and month: Dec. 31st of the year
- Further adjust by selecting the earlier of the imputed date, death date, and post-treatment end date*.

Post-treatment end date* is defined as the last visit date or the discontinuation of study day, whichever is later.

Completely missing end date:

- AE end date will be left as missing
- Medication end date will be imputed as earlier of death date and post-treatment end date (as defined above).

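### The SAP's concomitant-medication rule leaves out drugs that start on the first-dose date, and the imputation of missing start dates puts some undated drugs on that date

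*SAP*

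**What the plan says.** SAP 2.5 sets three rules around the date of first dose in BORA.

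- **Concomitant:** either of two conditions suffices, "if the start date is after the date of first dose in BORA, or if it started prior to the date of first dose", the second also requiring that use continued afterwards. Starts later than the on-treatment period are excluded.
- **Prior:** "An asthma medication will be regarded as prior if it was stopped on or before the date of first dose for the study". This rule is worded for asthma medication only.
- **Baseline maintenance asthma medication:** "if it started prior to or on the date of first dose of IP in BORA and was ongoing after the first dose of IP".

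SAP Appendix B (8.2) states that its date imputation serves the prior/concomitant classification. A completely missing start date takes the end date if the drug ended before Visit 1. In every other case it becomes the Visit 1 date. For example: "If AE end date or medication end date is after the first visit date (Visit 1), then impute the start date as the first visit".

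Protocol 4.1.1 says that the predecessor study's end-of-treatment visit and BORA Visit 1 "will occur on the same day and will include the first dose of IP for this study". A patient who cannot be dosed at that visit cannot enrol.

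SAP 4.2.3 tabulates, by treatment group, the patients taking concomitant medications and "those who take disallowed concomitant medications during the study". The same summaries are repeated for patients who moved on to MELTEMI.

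**The concern.** One limb of the concomitant rule is strictly after the first-dose date and the other strictly before it, so the date itself belongs to neither. This does not look like shorthand, because the maintenance rule in the same section expressly includes the day. The adverse-event on-treatment period in SAP 3.1.1 also includes it. As written, a reaction on the first-dose day is on-treatment while the drug given for it that day is not concomitant.

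For patients from a predecessor placebo arm, Visit 1 is the first benralizumab dose in these studies, and SAP 4.1 reports them as separate groups. Protocol 6.8 requires at least two hours of observation after each injection, so same-day treatment of a reaction is foreseeable. At stake is whether the by-group medication tables show such treatment, disallowed drugs started that day, and drugs of unknown start date that were in use during BORA.

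**Working it through.** The plan gives no figure on this point, so the check is one of date logic.

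**Inputs.** The three rules are from SAP 2.5 and the handling of missing start dates is from Appendix B. FD is the first-dose date, equal to Visit 1 by protocol 4.1.1. An end date later than FD is read as ongoing after first dose.

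**Rules as coded.**

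- Concomitant: start > FD, or (start < FD and end > FD).
- Prior (asthma drugs only): end ≤ FD.
- Baseline maintenance (asthma drugs only): start ≤ FD and end > FD.
- Start completely missing: use the end date if end < FD, otherwise FD.
- Amended concomitant rule: start ≥ FD, or (start < FD and end > FD).

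The prior and maintenance columns below use the current rules.

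| Recorded start / end | Start used | Concomitant now | Prior | Maintenance | Concomitant, amended |
|---|---|---|---|---|---|
| FD−30 / ongoing | FD−30 | yes | no | yes | yes |
| FD−30 / FD−5 | FD−30 | no | yes | no | no |
| FD−30 / FD | FD−30 | no | yes | no | no |
| FD / FD | FD | **no** | yes | no | yes |
| FD / FD+3 | FD | **no** | no | yes | yes |
| FD / ongoing | FD | **no** | no | yes | yes |
| FD+1 / FD+3 | FD+1 | yes | no | no | yes |
| missing / missing | FD | **no** | no | yes | yes |
| missing / FD−5 | FD−5 | no | yes | no | no |
| missing / FD | FD | **no** | yes | no | yes |
| missing / FD+100 | FD | **no** | no | yes | yes |

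**Results.**

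- All six patterns with a start on FD (three recorded, three imputed) fail the current rule. The amendment makes all six concomitant and leaves the other five unchanged.
- A drug started on FD and stopped later is neither prior nor concomitant.
- A drug started and stopped on FD is prior if it is an asthma drug. Otherwise it has no class, because prior is not defined for other drugs.
- If only the concomitant sentence is amended, the two patterns that start and end on FD would be both prior and concomitant for an asthma drug. The prior rule therefore needs a matching condition on the start date.

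**The case against.** The strongest reply is that little safety information depends on this table. Much of that stands, and it rules out several wider inferences.

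- **A reader might infer that first-dose reactions are lost.** They are not. SAP 3.1.1 includes the day of first dose in the on-treatment period, and SAP 4.2.5.1 summarises injection-site and hypersensitivity events separately. What is lost is the record of same-day treatment in one set of tables. Treatment begun the next day or later in the on-treatment period is counted.
- **A reader might infer that disallowed use is hidden.** SAP 2.2.1 identifies it by programming, for use during the treatment period, without relying on the concomitant definition. Deviations judged important are listed and tabulated.
- **A reader might infer that all undated drugs drop out.** Only completely missing start dates matter, and undated drugs that ended before Visit 1 are rightly excluded. Partial start dates go to the first of the month or to 1 January, so they reach the gap only if the first dose fell on that date. Background drugs are linked from the predecessor study (protocol 3.5.1), so a start date recorded there would carry over.
- **Asthma drugs that start on the first-dose date and continue** still appear in the baseline maintenance table.

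None of this closes the gap. No other SAP passage brings a first-dose-date start into the concomitant class. Bringing predecessor medications into the summaries adds records but does not change how they are classified.

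**Conclusion.** The rule is wrong as written, and its reach is modest. Every medication with a recorded or imputed start on the first-dose date is left out of the SAP 4.2.3 concomitant and disallowed-concomitant tables. An asthma drug that starts and stops that day is also mislabelled as prior. The number of such records is unknown and may be small, because the documents give no medication counts. The documents do not support a claim that the primary safety results, or any conclusion about the dosing regimens, would change.

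The conclusion assumes that the programming follows the literal text of SAP 2.5 and that Visit 1 is the dosing day, as protocol 4.1.1 requires.

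**What to change.** Change two sentences in SAP 2.5.

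1. *A medication is concomitant if it began on or after the BORA first-dose date, or began earlier and was still in use after that date.* The existing exclusion of starts after the on-treatment period stays.
2. *An asthma medication is prior if it began before the BORA first-dose date and was stopped on or before that date.*

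A drug that both starts and stops on the first-dose date is then concomitant only. Appendix B needs no change, because the undated drugs it moves to Visit 1 become concomitant under the first sentence.

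Prior should not be redefined as stopped before the first-dose date. A drug begun earlier and stopped on that date would then be neither prior nor concomitant, whereas the present rule correctly calls such an asthma drug prior.

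The cost is two sentences and one derivation. The small downside is that a few drugs taken on the first-dose day just before the injection will be counted as concomitant.
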